E. Potential Scientific Problems:

Adherence to the TRF protocol: This will be the first study to our knowledge that will assess the feasibility of using TRF in the context of a reduced calorie diet for weight loss. We will objectively measure compliance to the protocol at baseline and 12 weeks using CGM and photographic time-stamped food logs but will otherwise not know whether subjects randomized to the TRF group were compliant to the protocol. To limit the extent of possible non-compliance to the TRF arm we decided on a shorter intervention for our first study. We are also using a high intensity behavioral support program that will meet weekly to discuss dealing with hunger/cravings or other challenges that might be associated with TRF. We will also ask participants to keep a log documenting daily feeding duration (first and last energy intake events) during all intervention weeks.

F. Data Analysis Plan:

Sample Size Justification:. We will aim to recruit 60 participants in two cohorts.. The sample size was determined for the primary outcome, change in body weight (kg) at 12 weeks. Assuming 20% attrition, we will be left with n=48, or n=24 subjects per group. To justify the sample size, we computed the detectable difference that we have 80% power for based on existing preliminary and published data. We will assume an alpha=0.05 and use two-sample t-tests. We assumed that the RCD group will have similar weight loss as has been shown previously with the standard Colorado Weigh curriculum, in which the mean \pm standard deviation (SD) weight loss using an intent-to-treat analysis at 12 weeks is -4.1 \pm 3.7kg⁵⁷. There are no prior relevant data for 12-week weight loss using TRF in the context of a weight loss intervention. However, prior data from the Gill and Panda study²⁶ of time restricted feeding without a weight loss intervention showed a mean weight loss at 16 weeks of -3.3 kg with a SD=3.4 kg. Given that we are combining the RCD and TRF treatments, the standard deviation is likely to be between 3.4kg and the sum of the variation of the RCD and

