time restricted studies (SD of the sum = $\sqrt{3.7^2 + 3.4^2} = 5.0 \text{ kg}$). In our calculation, we assumed for the time restricted treatment group (RCD+TRF) a SD in-between the above lower and upper bounds of SD at 4.2kg. With these SD's, we have 80% power to detect a difference in mean weight loss between the two treatment groups of 3.5kg. This is slightly larger than the Gill and Panda study, but well within the range of the confidence interval of their result. In addition, this calculation is quite conservative. We will have power of 80% to detect an even smaller difference in weight loss between the groups, because in the final analysis we will adjust for baseline weight, which reduces the SD's in each of the groups and allows us to have power to detect smaller differences. The intervention will be modified if we are unable to recruit 30 participants, retain >70% of participants, or perform outcome measures within a 2-week window of the indicated time points in >90% of participants.

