Statistical Analysis: Efficacy Testing: Baseline demographic characteristics will be summarized by treatment groups using descriptive statistics. Any imbalance between groups will be examined using two-sample t-tests and Fisher's exact tests as appropriate. The primary analysis will use the ITT principle to test our study hypotheses under practical and realistic conditions when not all participants follow or complete the program. All randomized participants will be analyzed. A linear mixed effect model (LMM) will serve as the primary method to handle missing values. The normality assumptions will be evaluated and transformations used (e.g. square root and log) as appropriate. Change in weight is the primary outcome variable and others will be secondary outcomes. Consequently, no adjustment for multiple outcomes will be applied. P-values <0.05 will be considered significant. No interim analysis is planned. Any imbalance in baseline characteristics between groups that could potentially be a confounding factor for the outcome will be adjusted for in the statistical model (i.e., age, sex, level of PA achieved during intervention). Differences between groups in weight, fat mass, lean mass, MVPA, EI, sleep outcomes, and glucose variability will be compared using a LMM. Specifically, the test of time by group interaction will be used to assess efficacy. Pearson's correlations will be used to assess the relationship between sleep and nocturnal metabolism outcomes and longitudinal weight regain at 6 months. Variability of Major

Outcome Measures: Standard deviation and effect sizes will be determined based on the LMM model estimates to assist with planning the large-scale trial.

G. Summarize Knowledge to be Gained:

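### The efficacy model takes its covariates from observed imbalance, lists post-randomisation physical activity among them, and does not carry through the promised baseline-weight adjustment

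*Combined protocol and SAP*

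**What the plan says.** Section IV.F, Statistical Analysis: Efficacy Testing, makes two linked statements. On describing the groups: "Any imbalance between groups will be examined using two-sample t-tests" and Fisher's exact tests. On the model: "Any imbalance in baseline characteristics between groups that could potentially be a confounding factor for the outcome will be adjusted for in the statistical model". Age, sex and the level of PA achieved during the intervention follow in brackets. The text gives no size of imbalance that triggers adjustment, and does not say who judges potential confounding or when. Efficacy is the time-by-group interaction in a linear mixed model (LMM), with no covariates listed. The same paragraph takes standard deviations and effect sizes for the large trial from the LMM estimates.

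One paragraph earlier, the Sample Size Justification says that "in the final analysis we will adjust for baseline weight", without condition, and relies on this for its claim that a smaller difference than the stated one is detectable.

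Elsewhere PA is an outcome. Section IV.A lists it as a secondary outcome, the Exploratory Aim in Section I names it as a possible mechanism for group differences, and the efficacy paragraph itself compares moderate-to-vigorous PA between arms.

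**The concern.** In a randomised trial, baseline differences arise by chance. A test of them does not show which covariates matter for the outcome; prognostic strength does. If covariates enter according to what is seen after randomisation, the analyst settles the model with the data in hand.

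PA during the intervention is a more serious matter. It is measured after randomisation and may be affected by it. Section II (Innovation) cites a study in which eating or skipping breakfast changed PA energy expenditure. If time-restricted feeding changes PA and PA changes weight, adjusting for PA removes that part of the effect. If PA and weight loss share a cause such as motivation, adjustment can also distort the comparison, in a direction that cannot be known beforehand. Either result conflicts with the intention-to-treat comparison that the paragraph announces, and would pass into the planning of the large trial.

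The baseline-weight gap is simpler. The power section takes credit for a term that the model text does not contain.

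**Working it through.** **1. The plan's own figure.** Inputs from the Sample Size Justification: SD of weight change 3.7 kg (reduced-calorie diet, RCD) and 4.2 kg (RCD plus time-restricted feeding), 24 per arm, alpha 0.05 (two-sided assumed), 80% power. The standard error is √((3.7² + 4.2²)/24) = √(31.33/24) = 1.143 kg. The normal approximation gives 1.143 × (1.960 + 0.842) = 3.20 kg, and the exact t calculation 3.27 kg. The plan states "we have 80% power to detect a difference in mean weight loss between the two treatment groups of 3.5kg"; power at 3.5 kg is 85.0%. An SD of 4.2 kg in both arms gives 3.47 kg, a possible source of the stated value. The mismatch is conservative and separate from this point. I use 3.27 kg below.

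**2. What baseline weight could add.** These SDs are already SDs of change, so any further reduction needs a covariate that acts on change. With correlation r between baseline weight and weight change, the SE is multiplied by √(1 − r²). The documents give no r, so it is an assumption. Power was simulated at a true difference of 3.27 kg (100,000 trials per setting, 24 per arm):

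| r | √(1 − r²) | Detectable difference | Power: always adjusted | Power: only if baseline p<0.05 | Power: never adjusted |
|---|---|---|---|---|---|
| 0.2 | 0.980 | 3.20 kg | 80.8% | 79.9% | 80.0% |
| 0.3 | 0.954 | 3.12 kg | 82.7% | 80.1% | 79.9% |
| 0.5 | 0.866 | 2.83 kg | 89.2% | 81.0% | 80.1% |

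At r = 0.3 to 0.5 the SE falls by about 5 to 13%. The simulated spread of the estimates fell slightly less (1.143 to 1.104 at r = 0.3, or 3.4%; 1.142 to 1.001 at r = 0.5, or 12.3%), because the slope must be estimated. If entry depended on a 5% imbalance test, baseline weight would enter in about 5% of trials, and nearly all of the gain would be lost.

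**3. Type I error.** In the same simulation with no true difference, choosing baseline weight by a 5% pretest gave rejection rates of 4.9%, 4.8% and 4.4% at r = 0.2, 0.3 and 0.5. There is no inflation.

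**4. Chance flags.** If k independent baseline variables were each tested at 5% (the plan states neither a threshold nor a list), the chance of at least one flag is 1 − 0.95^k: 9.8% for 2, 14.3% for 3, 22.6% for 5 and 40.1% for 10.

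**5. PA as a covariate.** Suppose the arms differ by δ SDs in PA, and PA correlates r with weight change within arms. Adjustment then moves the estimate by r × δ × SD of change. The pooled SD is √((3.7² + 4.2²)/2) = 3.96 kg. With r = δ = 0.3 the shift is 0.3 × 0.3 × 3.96 = 0.36 kg; with r = δ = 0.5 it is 0.5 × 0.5 × 3.96 = 0.99 kg. Against the plan's 3.5 kg these are 0.36/3.5 = 10% and 0.99/3.5 = 28%. Both r and δ are illustrative.

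**6. Where the covariate sits.** If baseline weight is one of the LMM's repeated responses, a covariate that is constant within a person and enters only as a main effect shifts a participant's level, not the change. Simulated with 60 participants and three visits, adding age and sex moved the interaction by 0.000 kg with complete data. With 20% dropout it moved by 0.013 kg on average and 0.07 kg at most. The SE ratio was 1.000 in both. The same algebra applies to PA entered as one constant main effect. So steps 2 and 5 require covariates that act on change: a model for change or for post-baseline weight, a covariate-by-time term, or PA as a time-varying term. The plan does not say which applies.

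**The case against.** The strongest reply has four parts.

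- **Error rate.** A reader might infer that data-dependent selection invalidates the 5% level. The pretest simulation does not support that. A looser bound exists: an analyst free to fit all eight models from three optional covariates and report the most favourable would reach p<0.05 in about 9% (r = 0.2) to 11% (r = 0.3) of null trials. That bounds unlimited discretion; nothing in the documents indicates such a practice.
- **Chance flags.** A reader might take the 40% for ten variables as the plan's own risk. The plan names three variables, only two of them baseline, sets no 5% trigger, and also requires a judgement about confounding. That judgement makes the rule less mechanical, but it also leaves the choice more open.
- **Baseline weight.** A reader might infer that the plan intends to drop it. It does not: the commitment stands in the same section and is not withdrawn. The fault is two paragraphs that do not agree.
- **Stakes.** Specific Aim 1b concedes that the study lacks power to compare weight loss, and on the main-effects reading in step 6 age and sex hardly matter.

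These replies limit the size of the point. They do not answer the PA problem, since Aim 1b makes effect size and variability the products of the efficacy comparison. Nor do they supply a covariate list or a model form.

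**Conclusion.** The point holds in three limited parts. First, PA achieved during the intervention should not be in the primary adjustment set. It is post-randomisation, and the plan treats PA as an outcome and possible mechanism. The possible distortion is about 0.36 to 1.0 kg under the assumed values, of unknown direction, and arises only if PA is modelled so that it acts on change. Second, the covariates are not prespecified. Third, the baseline-weight adjustment behind the power claim is missing from the model text. At an assumed correlation of 0.3 to 0.5 the forgone reduction in SE is about 5 to 13%; at 0.2 it is about 2%. Inflated type I error is not demonstrated.

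**What to change.** In Section IV.F:

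- Remove PA during the intervention from the adjustment set of the primary model, and keep it for the exploratory mechanism analysis.
- Describe baseline balance by arm, and do not use tests to select covariates.
- Fix the covariates in advance, whatever the observed balance: baseline weight, age, sex and cohort. Cohort belongs because Section IV.C describes a change of meal-logging platform after Cohorts 1 and 2 and separate procedures for the cohort treated during COVID-19. State its levels, because the Sample Size Justification speaks of two cohorts.
- State a model in which these terms act on change, for example an LMM on post-baseline weight or weight change with baseline weight as a covariate. The efficacy test is then the group difference at 12 weeks. With post-baseline responses only, the time-by-group interaction would instead compare 12 weeks with the 6-month follow-up.
- Adjust each secondary outcome for its own baseline value.

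The cost is minor rewording and respecification of the model. All the variables are already collected. One consequence needs a sentence: a model of post-baseline values gives no direct weight to participants without any follow-up weight, so the text should say how this fits the commitment to analyse everyone randomised.

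### Physical activity achieved during the intervention is listed as a baseline covariate, so the weight comparison can become conditional on a post-randomisation outcome

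*Combined protocol and SAP*

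**What the plan says.** All of the rule stands in section IV.F, Statistical Analysis: Efficacy Testing.

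- Trigger: "Any imbalance in baseline characteristics between groups that could potentially be a confounding factor for the outcome".
- Action: such imbalance "will be adjusted for in the statistical model (i.e., age, sex, level of PA achieved during intervention".
- Earlier in the paragraph, straight after the sentence on summarising baseline demographics: "Any imbalance between groups will be examined using two-sample t-tests" (with Fisher's exact test as the alternative).
- Principle and analysis set: "The primary analysis will use the ITT principle" and "All randomized participants will be analyzed".
- Efficacy criterion in the linear mixed model (LMM): "the test of time by group interaction will be used to assess efficacy".
- PA as an outcome of the same model: the list of compared outcomes begins "Differences between groups in weight, fat mass, lean mass, MVPA".
- Use of the result: "Standard deviation and effect sizes will be determined based on the LMM model estimates", to help plan the large trial.

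Elsewhere, section IV.A lists accelerometer PA as a secondary outcome. The Exploratory Aim in section I names free-living PA among the possible mechanisms for a group difference, and section II (Innovation) plans to study how TRF affects PA. Section IV.C records PA for 7 days at baseline and again within 3 weeks after the 12-week programme.

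**The concern.** Age and sex cannot be changed by treatment, but achieved PA can. If the arms differ in it, the difference may be part of what RCD+TRF does and not confounding. Adjusting for it may then remove, or add, part of the effect under test. The more RCD+TRF changes PA, the more likely an imbalance rule is to bring PA into the model.

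Three things are at stake:

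- **The estimand.** The ITT statement asks for the effect of assignment when some people do not follow the programme. A PA-conditional contrast answers a different question. If PA and weight change share unmeasured causes, it is not a clean direct effect either.
- **The pilot's product.** Aim 1b and section IV.F pass effect size and variability on to the large trial, so the wrong quantity would be carried forward.
- **The analysis set.** Depending on coding, people without follow-up PA may leave the adjusted model.

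Applied to the MVPA outcome, the rule would also be circular.

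**Working it through.** **Inputs from section IV.F.** SD 3.7 kg (RCD) and 4.2 kg (RCD+TRF); 24 per arm after 20% attrition from 60; alpha 0.05 (two-sided assumed); difference 3.5 kg.

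**Assumptions not in the documents.** Correlation r between PA and weight change of 0.2 to 0.5; arm gap d in achieved PA of 0.25 to 0.5 SD.

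**The plan's own figure.** Pooled SD = √((3.7² + 4.2²)/2) = 3.96 kg. With 24 per arm, a t-test has 80% power at 3.27 kg and 85.1% power at 3.5 kg. The stated 80% at 3.5 kg is therefore conservative; an SD of 4.2 in both arms gives 3.47 kg. This point does not depend on that discrepancy.

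**Precision.** 95% CI half-width = 2.013 × 3.96 × √(2/24) = 2.30 kg.

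**Shift when PA is in the model, by how it enters:**

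1. *Change score on arm plus achieved PA, or PA-by-time in the LMM.* Shift = r × d × SD. Low: 0.2 × 0.25 × 3.96 = 0.20 kg. High: 0.5 × 0.5 × 3.96 = 0.99 kg.
2. *Time-constant PA main effect in a complete-data LMM.* Shift is nil, because the time-by-group term is untouched.
3. *Time-varying PA main effect (baseline and follow-up).* Take a baseline-to-follow-up PA correlation ρ = 0.5. If weight change tracks the follow-up PA level, the PA-change variance is 2(1 − ρ) = 1 and the slope is multiplied by (1 − ρ)/1 = 0.5. The shift is 0.10 to 0.50 kg. If weight change tracks the change in PA, the shift is r × SD × d/√(2(1 − ρ)). At r = 0.5 and d = 0.5 this is 0.99 kg for ρ = 0.5 and 1.28 kg for ρ = 0.7.

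A random-intercept LMM simulation (30 per arm, 1,500 runs per scenario, assumed baseline weight SD 15 kg, weight tracking PA level, ρ = 0.5, PA raised) gave these time-by-group estimates:

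| r, d | no PA | time-constant | time-varying | PA-by-time |
|---|---|---|---|---|
| 0.5, 0.5 | −3.49 | −3.49 | −3.01 | −2.52 |
| 0.2, 0.25 | −3.51 | −3.51 | −3.40 | −3.31 |
| 0.5, 0.5, 20% attrition | −3.47 | −3.47 | −3.00 | −2.50 |

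**If adjustment is triggered by a PA t-test at p<0.05.** The plan does not state this trigger. With 24 per arm, the noncentrality d√12 is 0.87 or 1.73, so adjustment is triggered in about 14% or 40% of trials. Change-score simulation, 40,000 trials per scenario, true effect 3.5 kg; each cell gives PA raised / PA lowered by RCD+TRF:

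| r, d | mean estimate when triggered (kg) | mean estimate, all trials (kg) | power, all trials (%) |
|---|---|---|---|
| 0.2, 0.25 | 3.30 / 3.66 | 3.43 / 3.57 | 82.9 / 86.0 |
| 0.2, 0.5 | 3.10 / 3.90 | 3.26 / 3.75 | 77.8 / 88.2 |
| 0.5, 0.25 | 2.98 / 4.00 | 3.32 / 3.69 | 82.7 / 89.5 |
| 0.5, 0.5 | 2.52 / 4.51 | 2.90 / 4.11 | 72.5 / 94.9 |

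With a zero total effect, rejection is 4.5% to 8.6%.

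**Unmeasured common cause.** Suppose 25% of the 3.5 kg runs through PA (slope 0.3 SD of weight change per SD of PA). The PA-adjusted estimate is then −2.60 kg, near the direct effect 0.75 × (−3.5) = −2.63. Adding an unmeasured cause of both PA and weight (loading 0.4) moves it to −2.18 kg.

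**Analysis set.** At 20% attrition, one time-constant follow-up PA value with missing rows dropped keeps 60 × 0.8 = 48 people. Time-varying PA with a baseline record keeps all 60.

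**The case against.** The strongest reply is that the sentence defeats itself. Its trigger is baseline imbalance, achieved PA is not a baseline variable, and so the literal condition never brings it in. What is certain is then a wording conflict; a biased contrast is only one possible outcome. This has force, but the parenthesis opens with i.e. and defines the covariates, nothing confines PA to a sensitivity analysis, and an analyst following the list would include it.

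The trigger is indeed assumed. The t-test sentence concerns baseline demographics, and the 0.05 threshold is not tied to adjustment. The triggering rates, all-trial means, power and rejection figures are therefore illustrative. The kilogram figures also depend on whether weight change follows the level of PA or its change. That widens the range upward and does not remove the problem.

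The loss of participants needs a coding the plan never specifies. The COVID-19 section keeps accelerometry by home drop-off while DXA, blood tests and RMR stop, so PA data are relatively protected. In the attrition check the estimate with time-constant PA did not move.

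Practical harm is limited. Aim 1b says the pilot is not powered for weight differences. Section IV.A lists weight as secondary, although section IV.F calls it primary. Both arms get the same 150 min/wk advice, so the PA gap may be small, and the illustrated shifts lie inside the 2.30 kg half-width. These points bear on severity, not on whether the text is wrong.

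**Conclusion.** The concern holds. A post-randomisation variable is named as a baseline characteristic to adjust for, and where the rule is followed the weight contrast can become PA-conditional, against the stated ITT principle. Confidence in this textual contradiction is high.

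The size runs from nil upward. Under the assumed correlations and gaps it is about 0.2 to 1.0 kg in a change-score or PA-by-time model. With time-varying PA it is about 0.1 to 0.5 kg if weight change tracks PA level, and up to about 1.3 kg in the PA-change case with ρ = 0.7. The estimate falls if RCD+TRF raises PA and rises if it lowers PA. The plan does not say how PA would enter the model, so the harmless form is not assured. This should be fixed, but it does not threaten the pilot's feasibility aims.

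**What to change.** In section IV.F, delete achieved PA from the parenthesis so that the efficacy-model covariates are age and sex. If a PA covariate is wanted, name baseline MVPA from the 7-day baseline recording; this is optional. Keep achieved PA as an outcome, and label any weight analysis adjusted for it exploratory.

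The cost is one phrase. Baseline MVPA is already collected, and sample size and visits do not change. The efficacy model would no longer account for differences in achieved PA. When the arms do not truly differ in PA and r = 0.5, simulated power is 84.8% without the rule against 85.6% with it, a loss of less than 1 point.

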- **Feasibility and tolerability of the interventions** assessed by enrollment and retention numbers, protocol related adverse events (AE's), and questionnaires assessing satisfaction, quality of life and mood.
- Adherence to interventions assessed both with self-report and with the use of a smartphone application in conjunction with continuous glucose monitoring.

Secondary Outcomes:

- Weight (scale) and body composition (DXA) obtained at baseline (prior to the weight loss intervention), at 12 weeks (following the weight loss intervention), and at a 6mo follow-up time point.
- Physical activity assessed by accelerometry
- Free-living sleep patterns assessed by wrist actigraphy
- Objective (in-laboratory) sleep recording using Compumedics Inc Siesta digital sleep recorders
- Meal timing and energy intake assessed by photographic food records
- Patterns in 24h glucose assessed by continuous glucose monitors over 7 days before and after the weight loss intervention
- Questionnaire based measures of appetite
- HqbA1c and lipids
- Resting metabolic rate and nocturnal energy metabolism by indirect calorimetery

B. Description of Population to be Enrolled:

Inclusion criteria.

- Adult males and females with a BMI of 27-45 kg/m² and weight stable over the previous 6 months;
- Age, 18-50 years old;
- Passing medical and physical screening, and analysis of blood and urine screening samples:
- Typical eating duration >12 hours per day (assessed by questionnaires);
- Own a smartphone
- Reside or work within approximately 30 minutes driving distance of CU-AMC (potential
 participants living outside of this driving distance could be included in the study at the PIs
 discretion).
- For participants in the optional Reproductive Hormone Sub-study: females, age 18-40, with regular menstrual cycles (between 18-40 days).

Exclusion criteria.

- Pregnancy or lactation for women (women who are >6 months postpartum with no plans of becoming pregnant in the next year and who are not currently lactating can be included; oral contraceptives will be allowed if medication has been consistent for the prior 6 months)
- Postmenopausal women (menopausal status will be assessed during the history and physical, with requirement of self-reported regular menstrual cycles for the last year; women who have undergone hysterectomy but with ovaries in place who continue to have regular menstrual symptoms can be included)

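### The efficacy test is an unspecified time-by-group interaction, which the plan does not tie to the 12-week weight comparison used for sizing

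*Combined protocol and SAP*

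**What the plan says.** Section IV.F, Sample Size Justification: "The sample size was determined for the primary outcome, change in body weight (kg) at 12 weeks", and "We will assume an alpha=0.05 and use two-sample t-tests". With 24 evaluable participants per arm the plan concludes that "we have 80% power to detect a difference in mean weight loss between the two treatment groups of 3.5kg". It adds that the final analysis will adjust for baseline weight.

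Section IV.F, Statistical Analysis: Efficacy Testing: "Change in weight is the primary outcome variable and others will be secondary outcomes", with no time point attached. Weight, body composition, activity, energy intake, sleep and glucose variability are compared by a linear mixed model, and "Specifically, the test of time by group interaction will be used to assess efficacy". The threshold is P<0.05. SDs and effect sizes for the future trial come from the same model.

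Section IV.A lists weight among the secondary outcomes, measured at baseline, "at 12 weeks (following the weight loss intervention), and at a 6mo follow-up time point". The 6-month follow-up assessments in IV.C repeat weight and DXA. Aim 1b names two targets: weight loss at 12 weeks and less regain over the following 6 months. It also states that the pilot is not powered for a weight-loss difference.

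**The concern.** With three scheduled visits, time-by-group interaction does not name one hypothesis. Depending on the visits included, the coding of time and the treatment of baseline, it can be the 12-week difference, a joint test of week 12 and month 9, a difference in slopes, or a difference in regain. These are different questions, and some give opposite signs on the same data. The 80% power in the sample size section belongs to the first of them only.

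Two things are at stake. A P<0.05 from this test need not mean a 12-week effect, and a P>0.05 need not mean its absence. The effect size carried into the future trial could also be a slope or a regain contrast, when that trial needs a 12-week difference. Leaving the choice open allows it to be made after the data are seen.

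**Working it through.** **Inputs from the plan.** n = 24 per arm; SD of 12-week change 3.7 kg (RCD) and 4.2 kg (RCD+TRF); alpha 0.05, taken as two-sided. The visits are placed at weeks 0, 12 and 39, the last from the week 1-39 programme heading. **Assumed, because the documents give no figure:** SD of the month-9 change (s39) 5-6 kg, and correlation (rho) of the two changes 0.6-0.8. Write d12 and d39 for the between-arm benefit at week 12 and month 9.

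**The plan's own figure.** SE = sqrt((3.7² + 4.2²)/24) = sqrt(31.33/24) = 1.143 kg. By the noncentral t with 46 df, 80% power falls at d12 = 3.27 kg, and 3.5 kg has 85.1%. The stated 3.5 kg is not reproduced from the stated SDs; 4.2 kg in both arms gives 3.47 kg. That discrepancy is conservative and separate from this point. The benchmark below is 3.27 kg.

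**Baseline and week 12 only, or a named week-12 coefficient.** The interaction is the difference in mean 12-week change. One simulated data set gave -3.473 kg and t = -3.295 by both routes, so nothing is lost.

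**Categorical time, three visits.** This is a 2-df test: F with 2 and 45 df, noncentrality (n/2)·d'V⁻¹d, where d = (d12, d39), V is the covariance of the two changes, and the pooled s12 = sqrt(31.33/2) = 3.958 kg. Example for a sustained 3.27 kg with s39 = 5 and rho = 0.7: 12 × 3.27²/(1 - 0.49) × (1/3.958² + 1/5² - 1.4/(3.958 × 5)) ≈ 8.3, giving about 70% power.

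**Linear time in weeks.** Mean time = (0 + 12 + 39)/3 = 17; sum of squares = 17² + 5² + 22² = 798. The slope difference is (-5·d12 + 22·d39)/798, so week 12 enters with a negative weight. The sign reverses once d39 < (5/22)·d12, which is 0.80 kg when d12 = 3.5 kg. With d12 = 3.5 and d39 = 0 it is -17.5/798 kg per week, or 0.86 kg over 39 weeks in favour of RCD.

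**Change in weight as outcome, week 12 and month 9 only.** The interaction is d39 - d12. A sustained benefit gives 0. A 3.5 kg benefit that halves gives 1.75 kg in favour of RCD.

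Power over the assumed grid, week-12 difference 3.27 kg unless stated:

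| Test | Sustained to month 9 | Halved | Gone |
|---|---|---|---|
| 12-week t-test | 80% | 80% | 80% |
| Categorical, 2 df | 70-72% | 73-89% | 88-99% |
| Linear in weeks | 34-51% | 9-12% (at 3.5 kg) | sign reversed |
| Change, post-baseline visits | 5% | sign favours RCD | sign favours RCD |

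With no week-12 difference and 3.5 kg at month 9, the 2-df test is significant 58-95% of the time.

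**The case against.** A reader might infer that no version of the interaction gives the 12-week comparison. That is not so. With baseline and week 12 alone it is exactly that comparison, and in a categorical three-visit model the week-12 coefficient is too. The analysis section does not itself say that three visits enter; that comes from the visit schedule. For accelerometry, actigraphy and glucose monitoring, which IV.C repeats after the 12-week programme and does not list at the 6-month visit, the interaction already is the 12-week contrast. This stands.

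A reader might also infer a general loss of power. The table does not support that. The 2-df test loses 8-10 points if the benefit is sustained and usually gains if it fades. At a sustained 3.5 kg it has 76-78%, close to the 80% that the plan claims. Nor does the text suggest linear time, and that row depends on the assumptions: with a month-9 SD of 4 kg, sustained power is 68-73%. The change-score model is not stated either. It remains possible because the plan names change in weight as the outcome and promises baseline adjustment.

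A month-9 effect is not an error, since Aim 1b includes regain, and a joint test speaks to both targets. It still cannot say which target was met or in which direction. The pilot status limits the consequence: Aim 1b disclaims power, IV.A lists weight as secondary, and the triggers for modifying the intervention are recruitment, retention and visit timing. It does not remove the point, because IV.F calls weight change primary, sets a significance threshold and draws the next trial's effect size from this model.

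**Conclusion.** The point holds as a mismatch between sizing and analysis. The text does not secure the 12-week comparison as the efficacy test, and applying the stated test to all scheduled weight visits neither isolates the week-12 effect nor gives it a direction. The slope weights, the reversed sign under linear time and the 5% result for a sustained benefit on change scores follow from algebra, given the visit times. The power ranges rest on the assumed month-9 SD and correlation and on 24 completers per arm. The documents do not support saying that the planned test is wrong under every reading, or that the trial has lost its stated power. Severity is moderate.

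**What to change.** Replace the interaction sentence in Statistical Analysis: Efficacy Testing with wording such as:

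> Time is categorical. Baseline weight is adjusted for as a covariate, or baseline means are constrained equal across arms. Efficacy for weight is judged by the single 1-df model-based difference between arms in change from baseline to week 12, with its 95% CI. The month-9 (or regain) contrast is reported separately as the second part of Aim 1b.

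State that the effect size and SD for the future trial come from these named contrasts. Use the same week-12 contrast for the other mixed-model outcomes that have a month-9 visit; those measured only at baseline and week 12 need no change. The cost is one paragraph of analysis wording and no new data.
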